Blood draws for clinical laboratory testing and urine collection for urinalysis will be performed at Day 1 and Months 1, 2, 3, 6, 9, 12, 15, 18, 21 and 24. Safety assessments of vital signs and listening to heart and lungs will be conducted at all visits. ECGs will be conducted on Day 1 and Months 1, 3, 6, 9, 12, 18 and 24.

For plasma biomarkers, plasma samples will be collected on Day 1 prior to dosing and on Months 3, 6, 9, 12, 15, 18, 21 and 24. Plasma markers include SavaDx, the complementary diagnostic/biomarker, and a subset of CSF biomarkers (NfL, neurogranin, total tau, $A\beta_{42}$ and YKL40). For the first 50 patients who provided a screening CSF sample, an additional CSF sample will be collected at Month 6 or Month 12 (25 patients each Month 6 and Month 12). This sample will be used to assess CSF biomarker changes. These CSF draws will, however, become OPTIONAL after 50 patients have provided either a Month 6 or Month 12 CSF sample. Further, these optional Month 6 or Month 12 samples should NOT be obtained from patients who did not provide a CSF sample at screening.

An independent Data Safety Monitoring Board (DSMB), will meet periodically to review patient safety assessments and determine if dosing may continue.

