7.1. STOPPING CRITERIA

Liver chemistry threshold stopping criteria have been designed to assure patient safety and to evaluate liver event etiology during administration of Study Drug. Administration of Study Drug will be discontinued if any of the following liver chemistry stopping criteria occurs:

- ALT or $AST \ge 3 \times ULN$.
- ALT or AST \geq 2.5 x ULN and total bilirubin \geq 2 x ULN.
- ALT or $AST \ge 2 \times ULN$ if associated with appearance or worsening of a rash or hepatitis symptoms (fatigue, nausea, vomiting, right upper quadrant pain or tenderness, fever, rash or eosinophilia).
- ALT or GGT \geq 2.5 x ULN that persists for \geq 4 weeks.

In the event of discontinuation due to liver abnormalities, the patient will be appropriately investigated to determine the potential cause and referred to a physician experienced in the treatment of hepatic disorders.

An additional stopping criterion will be bodyweight loss of ≥ 2 kg resulting in a BMI < 18.5.

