7.3. LABORATORY ASSESSMENTS

7.3.1. Clinical Laboratory Tests

The following clinical laboratory tests will be performed at screening, Day 1 predose, and at Months 1, 2, 3, 6, 9, 12, 15, 18, 21 and 24:

- Hematology: white blood cell (WBC) count with differential, red blood cell (RBC) count, hemoglobin, hematocrit, platelet count.
- Serum Chemistry: glucose, sodium, potassium, chloride, bicarbonate, calcium, phosphate, blood urea nitrogen (BUN), total bilirubin, creatinine, cholesterol, triglycerides, albumin, globulin, total protein, uric acid, alkaline phosphatase, alanine transaminase (ALT), aspartate transaminase (AST), gamma glutamyl transpeptidase (GGT), lactose dehydrogenase (LDH).
- Urinalysis: color, specific gravity, pH, protein, sugar, ketones, occult blood, creatinine clearance calculation by Cockcroft-Gault equation (without requiring a 24-h urine collection).

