3.2 General Considerations that Apply to All Phases

Analysis Populations

Three analysis sets are defined for each phase of the study.

- The Full Analysis Set (FAS) includes all patients who receive at least one dose of study treatment and have evaluable efficacy records at baseline and post-baseline visits.
- The Per Protocol Analysis Set (PP) is the same as the FAS minus patients with major violations of protocol inclusion or exclusion criteria, e.g., other or interfering neurologic disorders such as posterior cortical atrophy, frontotemporal dementia, multiple psychiatric diagnoses, taking anxiolytics, or significant history of cardiovascular disease. PP also excludes patients who refused assessments for one or more visits and patients who were < 65% compliant by pill counts.
- The Safety analysis set will include all patients who receive at least one dose of the study treatment. All safety analyses will be based on the Safety population. Patients will be analyzed as treated.

Defining Mild vs Moderate Baseline Severity

For the purposes of analyses in all phases of the study, mild AD is defined as baseline MMSE \geq 21, and moderate AD as baseline MMSE \leq 20.

Management of Analysis Data

All tables, listings and figures will be presented in landscape format. All outputs will be sent to CSI as electronic files in Rich Text Format (RTF) format documents.

Definition of Analysis Timepoints

Scheduled analysis visits are visits upon scheduled time points as specified in Table 1 Schedule of Time and Events.

Scheduled analysis visits during the study period will be windowed to the nearest scheduled visit within the same phase.

Unscheduled visits are visits with data not collected at scheduled time points. Unscheduled visits will be windowed to the nearest scheduled visit as described above.

For the purposes of calculating change from baseline in the tables, if there is an unscheduled visit with a value and the visit BEFORE the unscheduled visit (i.e., scheduled visit) does not have a value for that assessment, the value associated with unscheduled visit can be used. Else, disregard the unscheduled visit, if scheduled visit is available and has a value.

There will be one valid value of assessment kept for each scheduled analysis visit in summary / analysis statistics. All unscheduled visits will be included as collected in eCRF in listings.

Handling of Missing Data and Partial Dates

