4.7 Safety Analysis

Adverse Events

Treatment emergent AEs (TEAEs), defined as AEs that first occurred or worsened after first dose, will be summarized overall. Summary of TEAEs occuring in the Open-label phase (D1-M12 and M18-M24) will be summarized in one group . TEAEs occurring in Double-blind (RW) phase (M12-M18) will be summarized in other group. All the listings mentioned below to be provided for both the groups. The incidence of TEAEs will be reported as the number (percent) of patients with TEAEs within System Organ Class (SOC) and Preferred Term (PT). Patients will be counted only once within a SOC and PT, even if the patient experienced more than one TEAE within a specific SOC and PT. The number (percent) of patients with TEAEs will also be summarized by maximum severity and relationship. The denominators for calculating the percentages for summaries will be based on the number of patients in the analysis population enrolled to each group.

The following types of summary will be provided for Incidence of TEAEs:

- Treatment Emergent Adverse Events by System Organ Class and Preferred Term;
- Treatment Emergent Adverse Events by System Organ Class, Preferred Term and Maximum Severity;
- Treatment Emergent Adverse Events by System Organ Class, Preferred Term and Relationship to Study Drug;

The annualized incidence rate of AEs per person-years at risk, calculated as (365.25*number of AE occurrences)/(total treatment period with patients at risk of AE), will also be reported by most prevalent PT in the SOC.

The total period at risk for each patient will be defined as the period from first dose of study treatment to the date of the End of Treatment (EOT) (Month 12) or Early Termination (ET) visit for prematurely treatment discontinued patients. Annualized incidence rates will be expressed in terms of events per 100 patient years exposure.

Vital Signs

For Months 6, 12, 18, and 24, summary statistics will be provided (study population size, mean, SD, minimum, median, and maximum) for each vital sign parameter, by treatment group and overall. Summary statistics for change from baseline values will also be presented. Numbers and percentages of patients with abnormal values will be included.

ECG

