The 12-lead ECG tests will be summarized by treatment group and overall using qualitative statistics per each scheduled visit. The summary will include the number and percentage of patients with test values classified as normal, abnormal (clinically significant), abnormal (not clinically significant) and unevaluable.

Laboratory Data

For months 6. 12, 18, and 24, summary statistics will be provided (study population size, mean, SD, minimum, median, and maximum) for each laboratory test and their change from baseline by treatment group and overall, along with their change from baseline screening values will be presented overall, for each scheduled visit. Numbers and percentages of patients with abnormal values will be included.

Physical Examination

Full physical examination data will be listed overall, by enrollment group and patient only.

5 Analysis of Open-Label Phase

The following efficacy analyses will be applied to data from the OL phase (D1-M12).

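### SAP 4.7 leaves the visit scope of the laboratory tables unclear and plans no worst-value or stopping-criterion summary, so some on-drug liver peaks may be absent from the by-arm statistics

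*SAP*

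**What the plan says.** **Collection.** Protocol 7.3.1 lists ALT, AST, GGT and total bilirubin among the clinical laboratory tests, which "will be performed at screening, Day 1 predose, and at Months 1, 2, 3, 6, 9, 12, 15, 18, 21 and 24". That is ten visits after first dose.

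**Stopping rule.** Protocol 7.1 states that "Administration of Study Drug will be discontinued if any of the following liver chemistry stopping criteria occurs", and gives four criteria based on ALT, AST, GGT and bilirubin as multiples of the upper limit of normal (ULN). It adds a criterion on weight loss and BMI. None of these is tied to particular visits.

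**Laboratory tables.** SAP 4.7, Laboratory Data: "For months 6. 12, 18, and 24, summary statistics will be provided". These cover each test and its change from baseline, by treatment group and overall. The same sentence then says that change from screening "will be presented overall, for each scheduled visit. Numbers and percentages of patients with abnormal values will be included".

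**Vital signs.** SAP 4.7 names the same four months ("For Months 6, 12, 18, and 24, summary statistics will be provided"), whereas Protocol 4 says "Safety assessments of vital signs and listening to heart and lungs will be conducted at all visits".

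**Unscheduled values.** SAP 3.2 assigns them to the nearest scheduled visit. In change-from-baseline tables an unscheduled value may stand in when the preceding scheduled visit has none; otherwise it is ignored. "There will be one valid value of assessment kept for each scheduled analysis visit in summary / analysis statistics".

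**The concern.** Long-term safety and tolerability is the overall study objective in SAP 1.3, and the withdrawal phase has its own objective of comparing safety between simufilam and placebo. Protocol 2.2 reports adverse liver changes at the two higher doses of the 6-month rat study, and Protocol 7.1 is built around liver chemistry. A reader of the final report will want to know how many patients crossed those limits, when, and in which arm.

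Statistics taken at fixed months answer a different question. A patient who meets a criterion between the named months has drug stopped. By the next named month that patient's value is off drug, or missing if the patient has left. The peak on drug is the value that matters for safety, and it is the one least likely to fall in a four-month by-arm table. A worst-value summary does not have this weakness, and the SAP does not plan one.

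**Working it through.** The plan states no liver-event rate or expected count, so there is no figure to reproduce. The check is a visit count followed by a trace of where an elevation could appear.

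**1. Visits drawn against visits named** (Protocol 7.3.1; SAP 4.7)
- Open-label, to Month 12: drawn at 1, 2, 3, 6, 9, 12 (6); named 6, 12 (2); not named 1, 2, 3, 9 (4).
- Randomized withdrawal, to Month 18: drawn at 15, 18 (2); named 18 (1); not named 15 (1).
- Follow-up, to Month 24: drawn at 21, 24 (2); named 24 (1); not named 21 (1).
- Total: 6 + 2 + 2 = 10 drawn; 2 + 1 + 1 = 4 named; 4 + 1 + 1 = 6 not named.

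**2. Trace of a patient who meets a 7.1 liver criterion at Month 15 and stops drug**
- Four-month by-arm statistics: Month 15 is not included; the Month 18 value is off drug or absent.
- Change from screening: if this covers every visit and carries the minimum and maximum, the rise could show as the Month 15 maximum. It would be pooled over arms and would not be a multiple of ULN or a patient count. It could not show ALT or AST jointly with bilirubin, as the second 7.1 criterion requires.
- Abnormal-value counts: no visit and no threshold is stated, so a marginal value and one at a stopping limit may count alike.
- Adverse-event tables: the case enters if it is reported. SAP 4.7 puts withdrawal-phase events in one group and states no split by arm.
- Listings: the value is there, but a listing gives no rate.

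**3. Unscheduled and early-termination samples.** Assume each phase starts just after the previous phase's last visit and windows are set halfway between visits.
- Laboratory visits only: Month 6 takes 4.5 to 7.5 (3 months), Month 12 takes 10.5 to 12 (1.5), Month 18 takes 16.5 to 18 (1.5) and Month 24 takes 22.5 to 24 (1.5). Sum 7.5; 7.5 / 24 = 31%.
- All 14 scheduled visits after Day 1: 1.5 + 0.75 + 1.5 + 1.5 = 5.25; 5.25 / 24 = 22%.
- Withdrawal phase, either way: 1.5 of 6 months (25%) falls nearest to Month 18.

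So for 69% to 78% of the 24 months, such a sample would be assigned to a visit that is not named. These are shares of time, not of cases. The fourth liver criterion requires persistence for at least 4 weeks. After Month 3, scheduled chemistry is three months apart, so timely confirmation would need an unscheduled sample.

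**4. Contrast within SAP 4.7.** ECG results are summarized by treatment group at every scheduled visit. The four-month list applies only to laboratory data and vital signs.

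**5. Weight.** Protocol Appendix A records weight with vital signs for BMI. SAP 4.3 names weight and BMI as baseline characteristics, and SAP 4.7 plans no count for the 7.1 weight/BMI criterion.

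**The case against.** The strongest reply is that SAP 4.7 already reaches beyond four months. Its laboratory sentence extends change from screening to every scheduled visit, and the abnormal-value counts carry no visit limit. Protocol 10.4 promises only descriptive change from screening, so the SAP does not fall short of the protocol. A patient who meets a 7.1 criterion is investigated and referred, and would normally appear in the adverse-event tables and, if the patient leaves, among the reasons for early termination. The Data Safety Monitoring Board reviews safety separately. Protocol 2.2 reports no pathology findings in the nine-month dog study.

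Much of this stands, and it rules out several stronger readings that a reader might infer:
- That laboratory results are tabulated at four months only. The rest of the sentence contradicts this; the defect is unclear scope.
- That the worst liver values are lost. Those at the named months are tabulated, all are listed, and reported ones reach the adverse-event tables.
- That six unnamed visits out of ten means 60% of cases are missed. This would need crossings to be equally likely at every visit, which the documents do not say. Months 1, 2, 3 and 9 also precede randomization, so no arm comparison is lost there.
- That affected patients leave the study. Protocol 7.1 stops drug, not participation, and Protocol 8 requires laboratory tests at early discontinuation.
- That the liver rule makes the vital-sign tables deficient. It has no bearing on them; the only link is through weight, which the SAP's reference to each vital-sign parameter may already cover.

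The reply does not supply a by-arm summary at Month 15, a patient count against the 7.1 limits, or a rule that keeps the worst value when two exist for one visit.

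**Conclusion.** The point holds as a reporting gap. By-treatment laboratory statistics are named for four of ten post-dose visits, in a sentence whose scope is unclear. No worst-value or 7.1-criterion summary is planned, and a worse unscheduled value gives way to a scheduled one in change-from-baseline tables. For the blinded comparison the gap is one visit of two, Month 15, and the SAP states no arm split for withdrawal-phase adverse events that would make up for it.

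The visit counts are exact. How many patients are affected is unknown: it depends on how many crossings occur, when they occur, and whether the each-visit wording is read broadly. A downward bias in the reported rate of liver abnormality is therefore possible but not shown. Because long-term safety is the main objective and the remedy is cheap, the change should be made.

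**What to change.** In SAP 4.7:
1. Reconcile the Laboratory Data sentence so that the tables cover every scheduled laboratory visit, by arm in the withdrawal phase. State the visits and the definition of abnormal that apply to the abnormal-value counts.
2. Add a table of each patient's worst on-treatment value for ALT, AST, GGT and total bilirubin, over scheduled, unscheduled and early-termination samples, by period and by withdrawal-phase arm. Exempt it from the one-value-per-visit rule in SAP 3.2.
3. In the same layout, give the number and percent of patients meeting each existing Protocol 7.1 liver criterion, including the combined ones, and the weight/BMI criterion.

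The cost is SAP wording, programming and a few extra tables from data already collected. There is no patient or site burden, no effect on sample size, and no change to any clinical rule. SAP 1.1 already allows further analyses at the sponsor's request, but as post hoc; writing these into the plan avoids that label.

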7.2. EVALUATIONS BY VISIT

7.2.1. Screening Visit 1 (Days -29 to 0)

Patients who completed PTI-125-02 < 60 days of study start will not be rescreened but will sign the ICF on Day 1 or earlier for this open-label extension.

For all other patients, the following will be completed in the screening visit:

- Informed Consent
- Review of Inclusion and Exclusion Criteria
- Medical history
- Review of concomitant medications
- Confirmation that the patient is either fully vaccinated for the COVID-19 virus at least 2 weeks prior to first dose of simufilam, or a positive serology test for the COVID-19 virus with no current symptoms
- If needed, CT scan to confirm I/E criteria, per investigator judgement
- MMSE-2 evaluation (prior patients do not need to meet 16 to 26 range)
- Columbia Suicide Severity Rating Scale (C-SSRS)
- Physical examination, including measurement of vital signs (blood pressure, temperature, pulse and respiratory rate), height, weight
- A 12-lead ECG (5-min supine)
- Laboratory assessments, including serum chemistry, hematology, urinalysis, and screens for HCV, HIV and HBsAg.
- Urine drug screen.

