10.4. SAFETY ANALYSIS

Adverse events reported on case report forms will be mapped to preferred terms and organ systems using the MedDRA mapping system. Vital signs and clinical laboratory results will be descriptively summarized in terms of change from screening values.

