1.3 Study Objectives

The overall study objective is to assess the long-term safety and tolerability of simufilam.

This study has separate sets of objectives for the OL and RW phases. Safety and tolerability are the primary objectives of the OL phase. The primary objective of the RW phase is to assess patient response to blinded, randomized drug withdrawal.

Because drug safety in non-responders can be a critical component of a drug's risk-reward assessment, all patients who completed the 12-month OL phase were eligible to enter the RW phase, regardless of whether they previously showed an apparent response (or not) to open-label drug treatment.

Some study objectives overlap in the OL and RW phases. Hence, objectives are summarized separately below for the OL and RW phases, and for objectives spanning multiple phases. All objectives apply to mild-to-moderate Alzheimer's Disease (AD) patients, 50-85 years of age.

Objectives for the Open-label (OL) phase

- Assess the long-term safety and tolerability of OL treatment with simufilam 100 mg b.i.d. during 12-month repeat-dose oral administration.
- Assess mean changes from baseline on MMSE and compare those changes between patients with mild vs moderate AD.

Objectives for the Randomized Withdrawal (RW) phase

- Assess the safety and tolerability of treatment with simufilam 100 mg b.i.d. versus matching placebo over the 6-months study period.
- Assess patient response to blinded, randomized drug withdrawal on ADAS-Cog11.

Objectives Spanning Overall Study

Exploratory objectives tested across multiple phases are to:

- Characterize the safety and tolerability of simufilam during and up to 24 months of treatment.
- Assess mean changes from baseline on biomarkers and compare those changes between patients with mild vs moderate. For CSF biomarkers, change from baseline to M6 or M12 will be calculated. Plasma biomarkers will be analyzed for change from baseline to M6 and M12 for the OL phase and from M12 to M18 for the RW phase.

Note: All biomarker assessments in this study are exploratory endpoints that are not patient safety related, are 'Research Use Only' products, and, hence, are not intended to be compliant with FDA's Quality System Regulation (QSR) or ISO equivalent.

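### SAP 4.7 sets no randomized-withdrawal baseline for laboratory and vital-sign change, so Month 18 change by arm would probably run from study entry and miss the 6-month placebo comparison

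*SAP*

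**What the plan says.** **Visits and columns.** The vital-signs paragraph of SAP 4.7 reads "For Months 6, 12, 18, and 24, summary statistics will be provided", with results "for each vital sign parameter, by treatment group and overall", and adds "Summary statistics for change from baseline values will also be presented". The laboratory paragraph names the same four months and gives results "for each laboratory test and their change from baseline by treatment group and overall, along with their change from baseline screening values". That sentence continues by saying that the screening-based change is shown overall, for each scheduled visit. The lead-in to SAP section 4 says that its analyses are summarized overall, which does not fit the by-arm wording.

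**Reference point.** SAP 4.7 does not define baseline. Protocol 10.4 says "Vital signs and clinical laboratory results will be descriptively summarized in terms of change from screening values" and does not mention arms. SAP 2.2 lists vital signs and clinical laboratory tests among the pre-dose Day 1 baseline measures, and SAP 4.5 equates baseline with Day 1. A separate RW baseline (Month 12, or Withdrawal Day 1 for patients kept on open-label drug) appears in SAP section 6, where it governs efficacy analyses.

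**Objective and grouping.** One RW objective in SAP 1.3 is "Assess the safety and tolerability of treatment with simufilam 100 mg b.i.d. versus matching placebo over the 6-months study period". For the Safety set, SAP 3.2 says "Patients will be analyzed as treated".

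**Screening.** Under Protocol 7.2.1, patients who completed PTI-125-02 within 60 days of study start "will not be rescreened but will sign the ICF on Day 1 or earlier for this open-label extension".

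**The concern.** The RW phase is the only part of the study with a concurrent placebo group, and safety against placebo over those 6 months is a stated objective. SAP 4.7 groups adverse events by phase and states no split by arm. The laboratory and vital-sign tables are therefore the only safety outputs for which change is planned by arm.

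If that change is counted from study entry, the Month 18 columns mix two things: a year or more of open-label treatment that both arms shared, and the RW months in which they differed. A laboratory shift that developed on simufilam and reversed on placebo, or that appeared only after withdrawal, would be hard to see in the within-arm figures. Those figures are what a reader of a descriptive table looks at first.

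Two smaller problems follow from the same wording. A screening reference is not available in this study for patients exempt from rescreening. And treatment group has no stated meaning at Months 6, 12 and 24, when every patient is on open-label simufilam.

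**Working it through.** The plan states no figure for these tables, so there is none to reproduce. The check is a timeline, followed by arithmetic under stated assumptions.

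**1. Treatment at each tabulated visit** (SAP 2.2; Protocol 7.2.8)

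| Visit | Treatment leading up to the visit |
|---|---|
| Month 6 | open-label simufilam, all patients |
| Month 12 | open-label simufilam, all patients; the morning clinic dose is still open-label and the randomized bottle starts that evening |
| Month 18 | simufilam or placebo |
| Month 24 | open-label simufilam, all patients |

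Of the four listed months, only Month 18 follows differing treatment.

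**2. What a change from Day 1 to Month 18 contains.** 12 of 18 months (12/18 = 67%) is identical treatment in both arms. The share is larger for patients who waited on open-label drug for RW supply.

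**3. Which pre-RW value exists.** Laboratory tests and vital signs are scheduled at Month 12, before the first RW dose. The Withdrawal Day 1 visit (Protocol 7.2.9 and Appendix A) schedules neither. For waiting patients the last scheduled pre-RW value is therefore also Month 12.

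**4. Spread of the change score.** Assume equal variance σ² at each visit. Let ρ₀ be the correlation of the Month 18 value with Day 1, and ρ₁₂ its correlation with Month 12. Then SD(change) = σ√(2(1 − ρ)), and the ratio of the two SDs is √((1 − ρ₀)/(1 − ρ₁₂)). The documents give no correlations, so these are assumed:

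| ρ₀ | ρ₁₂ | SD ratio, Day 1 to Month 12 reference |
|---|---|---|
| 0.8 | 0.85 | √(0.20/0.15) = 1.15 |
| 0.7 | 0.8 | √(0.30/0.20) = 1.22 |
| 0.5 | 0.7 | √(0.50/0.30) = 1.29 |
| 0.6 | 0.8 | √(0.40/0.20) = 1.41 |
| 0.4 | 0.7 | √(0.60/0.30) = 1.41 |

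The more extreme pairing of 0.5 with 0.8 gives √(0.50/0.20) = 1.58. If ρ₀ = ρ₁₂ the ratio is 1 and nothing is lost.

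**5. Bias and reading within arms.** Assume that a value rises 0.5 SD on open-label drug, holds on simufilam, and falls 0.4 SD on placebo. The means are then 0 at Day 1 and 0.5 at Month 12. At Month 18 they are 0.5 (simufilam) and 0.5 − 0.4 = 0.1 (placebo).

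| Reference | Simufilam change | Placebo change | Difference |
|---|---|---|---|
| Day 1 | 0.5 − 0 = +0.5 | 0.1 − 0 = +0.1 | 0.4 |
| Month 12 | 0.5 − 0.5 = 0 | 0.1 − 0.5 = −0.4 | 0.4 |

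A simulation of 20,000 trials under these assumptions, with 78 patients per arm (220 − 43 − 21 = 156, split 1:1), gave a mean difference of 0.40 with either reference. The contrast is unbiased because both references precede randomized treatment. The within-arm picture changes: from Day 1, the placebo arm's fall of 0.4 prints as a rise of 0.1.

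**The case against.** The strongest reply is that this is a request for clarification. The tables are descriptive. SAP 4.7 plans no test or interval for arm differences in these data, the Month 18 contrast is unbiased from either reference, and Month 18 values and abnormal counts by arm do not depend on the baseline. With Month 12 and Month 18 values both shown by arm, a reader can already see the shift in means, apart from dropout. All of that stands. It also means that statements about wider intervals or lost patients would describe no planned output.

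Three stronger readings are tempting and are not supported:

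- *Screening is the stated reference for the by-arm tables.* The laboratory sentence attaches the screening change to the overall presentation, and Protocol 10.4 does not mention arms. The by-arm reference is undefined, and study entry is only its likely reading.
- *Simufilam data will be labelled placebo.* No text fixes a column heading, and the as-treated rule in SAP 3.2 points the other way.
- *Patients never randomized drop out of the tables.* They remain in the overall column.

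Arm columns outside the RW phase can also be legitimate. At Months 6 and 12 they show whether the later arms were comparable. At Month 24 they contrast continuous with interrupted dosing, which SAP 1.3 and 7.1 name for efficacy.

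The reply does not answer the main point. The SAP defines an RW baseline for efficacy and none for safety, and change over the RW months is what the RW safety objective calls for.

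**Conclusion.** The point holds as a should-fix matter of method, a little more than missing detail. As written, Month 18 change by arm would most likely be measured from study entry. It would then include at least 12 months of common open-label treatment and would not show change over the 6-month RW comparison.

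The cost is in precision and readability, with no bias. The SD of change is 1.15 to 1.41 times larger over the main assumed correlations, provided that values correlate more strongly over 6 months than over 18. Within-arm changes can hide or reverse the direction of what happened after withdrawal. The correlations and effect sizes are assumptions. The study-entry reading is an inference from Protocol 10.4 and from SAP 2.2 and 4.5. No efficacy conclusion depends on this.

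The screening reference in Protocol 10.4 is a separate and smaller defect. It fails for patients exempt from rescreening, whose number the documents do not give, while Day 1 pre-dose values are scheduled for everyone.

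**What to change.** In SAP 4.7:

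- **(a) RW visits by arm.** Compute change from the last value at or before the first RW dose. This is normally Month 12, including for patients who had a Withdrawal Day 1 visit.
- **(b) Open-label and overall tables.** Use the Day 1 pre-dose value as the reference in place of screening. Align Protocol 10.4, or record the departure in the SAP, where SAP 1.1 says that departures from protocol methods are to be explained.
- **(c) Labels.** Mark Months 6, 12 and 24 as open-label simufilam. Head any arm columns at Months 6 and 12 as later randomized arm, for comparability only. Head those at Month 24 as continuous versus interrupted dosing. Keeping Month 12 by arm is useful, because it is the reference for (a).

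While editing, reconcile the by-arm wording with the overall-only lead-in to section 4. Also state whether RW laboratory data at Month 15 and vital signs at Months 13 and 15 are tabulated: they are collected but are not among the listed months, although the laboratory sentence also refers to each scheduled visit.

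The cost is SAP wording and one extra baseline flag in the analysis datasets. All the values are already in the visit schedule.
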